9.5. Lead-in Period

The 2-week lead-in period of the trial includes the interval between Visit 2 and Visit 4.

Subjects' current diet (particularly caloric intake) and exercise levels will be reviewed during lead-in and at subsequent visits throughout the study, as needed, to assess adherence to the lifestyle advice discussed at Visit 2 (Week -2) as part of subject training and education. Subjects should be encouraged to eat 3 meals a day plus a snack before bedtime (21 grams CHO Extend Bar®, Extend Nutrition, St. Louis, MO or equivalent) to support U-500R dosing per CSII or MDI during the study.

Subjects will continue taking prestudy AHAs and doses (per inclusion/exclusion criteria in Sections 8.1 and 8.2 and allowed concomitant therapies in Section 9.11) and should not discontinue or change doses during the study. Refer to Study Schedule for details of events (Attachment 1).

9.6. Randomization

At Visit 4 (Week 0), if subjects have been re-confirmed for trial eligibility (Section 8), they will be randomized at a 1:1 ratio to the two treatment arms (CSII or MDI) using IWRS (Section 9.3). Subjects will be stratified by entry HbA1c $\geq 8.5\%$ or $< 8.5\%$, nonusers versus users of GLP-1 receptor agonists or SGLT2 inhibitors, and U-500R at entry versus other insulins.

Subjects in the study will continue taking noninsulin pre-study AHA regimens (per inclusion/exclusion criteria in Sections 8.1 and 8.2) and allowed concomitant therapies. Subjects should not discontinue or change doses during the study (Section 9.11). Subjects will transition to U-500R MDI for 2 weeks and then initiate 24 weeks of CSII or MDI treatment (Section 9.7).

Subjects who discontinue prior to randomization will be considered screen failures. No ET activities will be applicable.

9.7. Transition to U-500R MDI

All subjects will administer U-500R MDI delivered TID (40:30:30 unless otherwise noted) during the transition period (Weeks 0-2). Transition to U-500R MDI will follow the criteria below in Table IBHD.9.3. Subjects will have their insulin adjusted weekly by the investigator using the algorithm from Section 9.8.2.1.

Table IBHD.9.3. Transition from entry insulin to U-500R MDI

Insulin Regimen (Screening)	HbA1c (Screening)	Mean SMBG (Screening to Week 0)	Conversion from Screening TDD to U-500R TID Dose
Insulin with or without U-500R	>8%	>183 mg/dL	1:1
Insulin with or without U-500R	>8%	≤183 mg/dL	Reduce TDD by 20%
Insulin with or without U-500R	≤8%	--	Reduce TDD by 20%
U-500R only	--	--	1:1

Abbreviations: HbA1c = hemoglobin A1c; SMBG=self-monitored blood glucose; MDI = multiple daily injections; TID= three times daily; TDD=total daily dose.

Subjects treated with U-100 and/or other concentrated insulin (with or without U-500R) at screening Visit 1 (Week -3) with HbA1c levels >8% and a mean SMBG (recorded prior to Visit 4 [Week 0]) value >183 mg/dL (corresponding to HbA1c value of >8.0% [estimated average glucose; Nathan et al. 2008]) at Visit 4 should be transitioned to U-500R using 1:1 dosage conversion.

Subjects treated with U-100 and/or other concentrated insulin (with or without U-500R) at screening Visit 1 (Week -3) with HbA1c levels >8% and a mean SMBG (recorded prior to Visit 4 [Week 0]) value ≤183 mg/dL (corresponding to HbA1c value of ≤8.0%) at Visit 4, should transition by reducing their U-500R TDD by 20%.

Subjects treated with U-100 and/or other concentrated insulin (with or without U-500R) at screening Visit 1 (Week -3) with HbA1c ≤8% should transition to U-500R at Visit 4 (Week 0) by reducing their U-500R TDD by 20%, regardless of SMBG value.

Subjects treated with U-500R insulin only at screening Visit 1 (Week -3) should transition to U-500R TID with proportion 40:30:30 using a 1:1 dosage conversion at Visit 4 (Week 0), regardless of HbA1c and/or SMBG. Those subjects already on U-500R TID at entry can continue their pre-entry U-500R TID proportions at the discretion of the investigator.

Investigators may also deviate from the proportion, if deemed necessary, for the safety or well-being of the subject (that is, due to a safety concern). Any major deviation from the recommended proportion must be discussed with Lilly CRP/CRS.

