7.1.4. Screening Period

This study contains a 1-week screening period between Visit 1 (Week -3) and Visit 2 (Week -2), which allows for the evaluation and assessment of potential subjects' eligibility against the inclusion and exclusion criteria (Sections 8.1 and 8.2, respectively). Subjects may be prescreened for inclusion/exclusion criteria that are available from their subject files, including any laboratory values on file collected within the previous 30 days, in compliance with local privacy regulations. Subjects will continue their pre-study insulin and AHA regimens and doses (per inclusion/exclusion criteria in Sections 8.1 and 8.2). Refer to [Attachment 1](#) for the study schedule of screening period activities.

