7.1.5. Lead-In Period

Eligible subjects will begin a 2-week lead-in period at Visit 2 (Week -2) according to the Study Schedule ([Attachment 1](#)). The lead-in period is intended to stabilize HbA1c related to study effect (Gale et al. 2007) and verify insulin dose. Subjects entering the trial at Visit 1 will continue their pre-study insulin regimen. Subjects will also continue taking pre-study AHA regimens and doses (per inclusion/exclusion criteria in Sections 8.1 and 8.2) and should not discontinue or change doses during the study, apart from specific instructions provided in Section 9.11.

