7.1.7.1. Transition to U-500R MDI

A 2-week transition period is included in the 26-week treatment period and will follow randomization. The transition period is intended to transition all subjects safely from their current insulin regimen to U-500R TID 40:30:30 (Section [9.5](#)), and to titrate U-500R according to the TID algorithm (Section [9.8.2.1](#)). The highest 24-hour TDD from the past 3 days will be utilized for calculation of the U-500R TID dose and the dose split into the ratio of 40:30:30. Those subjects already on U-500R TID at entry can continue their pre-entry U-500R TID proportions at the discretion of the investigator. At Visit 6 through Visit 17 or ET, subjects will be treated with either U-500R CSII (Section [9.8.1.1](#)) or U-500R MDI delivered TID (Section [9.8.2.1](#)) based on titration algorithms and the treatment to which they are randomized.

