9.4. Rationale for Selection of Doses in the Study

Protocol IBHD dosing transition to U-500R MDI and titration regimens for the CSII and MDI treatment groups are guided by initial insulin TDD (based on the highest TDD recorded in the 3 days before Visit 4), screening HbA1c (Visit 1), subsequent glucose monitoring, literature expert reviews (Lane 2006; Lane et al. 2009; Hirsch 2010, Lane et al. 2010; Segal et al. 2010; Reutrakul et al. 2012), efficacy and safety results from one Phase 4 clinical study (B5K-US-IBHC [Hood et al, 2015]), results from simulations performed using a systems physiology model of diabetes (Entelos PhysioLab® Modeler) based on data from previous pharmacodynamics/pharmacokinetics studies (de la Peña et al. 2011) of U-500R and U-100 Humulin regular insulin) and on expert protocol consultant advice.

Fasting and bolus for CSII and MDI therapy plasma-equivalent glucose target ranges are 80 to 140 mg/dL. Recommended administration of U-500R bolus doses, within approximately

30 minutes before meals by CSII or MDI dosing, is based on label advice and recent pharmacodynamics/pharmacokinetics study results in obese, healthy subjects that demonstrate both prandial and basal activity of U-500R (de la Peña et al. 2011). Administration of U-500R bolus doses 15 minutes before meals will be assessed in a subset of subjects participating in the continuous glucose monitoring (CGM) addendum to demonstrate glycemic impact. If the shorter bolus time period is found to be equally efficacious, there may be a potential benefit on adherence.

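### Table IBHD.9.3 converts the U-500R starting dose from the screening TDD, Sections 7.1.7.1 and 9.4 use the highest TDD of the last 3 days, and the protocol does not say which applies

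*Protocol*

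**What the plan says.** Section 9.7 makes the table the operative instruction: "Transition to U-500R MDI will follow the criteria below in Table IBHD.9.3". The dose column of that table is headed "Conversion from Screening TDD to U-500R TID Dose", and its entries are either a 1:1 conversion or a 20% reduction. The paragraphs below the table say who gets which factor. For example, subjects not on U-500R alone with a screening HbA1c of 8% or less "should transition to U-500R at Visit 4 (Week 0) by reducing their U-500R TDD by 20%, regardless of SMBG value". None of those paragraphs says on which days the TDD is measured.

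Section 7.1.7.1, on the same transition, gives a different base: "The highest 24-hour TDD from the past 3 days will be utilized for calculation of the U-500R TID dose". Section 9.4 describes the initial TDD as "based on the highest TDD recorded in the 3 days before Visit 4".

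On timing, Section 7.1.4 defines screening as the week from Visit 1 (Week -3) to Visit 2 (Week -2). Section 9.5 then adds: "The 2-week lead-in period of the trial includes the interval between Visit 2 and Visit 4". Section 7.1.5 gives one purpose of the lead-in as to stabilize HbA1c "and verify insulin dose".

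**The concern.** The sources differ in two ways. The table names a TDD from screening. The other two sections name a maximum over 3 days, which Section 9.4 places immediately before Visit 4. A site working from Section 9.7 and a site working from Section 7.1.7.1 could each be fully compliant and still give the same subject different first doses.

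This rule applies to every randomized subject in both arms, because all of them go through the MDI transition. The product is five times as concentrated as U-100 insulin (Section 9.7.1). At stake is whether the first dose is set consistently and safely. A monitor also has no single rule against which to call a starting dose an error, although SAP Table IBHD.5.1 lists dosing error among its deviations.

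**Working it through.** The plan states no figure that depends on this point, so there is nothing to reproduce. The check is a comparison of texts, followed by an illustration.

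**Can 'screening' in the heading simply mean Visit 4?** The text does not support that. Section 7.1.4 ends screening at Visit 2, and the 2-week lead-in lies between Visit 2 and Visit 4. The same table also separates the two ideas: its HbA1c column is labelled as screening, while its SMBG column runs from screening to Week 0.

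**How far apart are the time points?** The heading names no visit. From Visit 1 the nominal gap is 0 - (-3) = 3 weeks; from Visit 2 it is 0 - (-2) = 2 weeks. Hence about two to three weeks.

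**Does any other passage settle it?**
- Section 9.8.2 sends MDI subjects to Section 9.7 for the initial dose, which leads back to the table.
- Section 9.7 does not refer to Section 7.1.7.1 or 9.4.
- Section 7.1.7.1 cross-refers to Section 9.5, which covers the lead-in and contains no TDD rule.
- The discretion in Section 9.7 covers the split proportions, not the TDD source.
- Section 9.8.1 states its TDD base clearly, but for the CSII start at Visit 6.

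**Do the documents treat the two TDDs as distinct?** Yes. Section 8 re-confirms the TDD criterion before randomization at Visit 4. SAP Table IBHD.5.1 has one row for TDD out of range at Visit 1 (kept in the per-protocol set) and another for Visit 4 (excluded from it).

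**Size.** Let S be the screening TDD, H the highest 3-day TDD, and f the conversion factor (1.0 or 0.8 from the table).

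- Starting dose by the table = f × S; by Sections 7.1.7.1 and 9.4 = f × H.
- Difference = f × (H - S).
- Relative difference = H/S - 1, because f cancels.

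The documents give no value for H - S. As an assumption, take S = 300 U and H = 300, 330 or 360 U:

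| H (U) | f | f × S (U/day) | f × H (U/day) | Difference (U/day) | Relative |
|---|---|---|---|---|---|
| 300 | 1.0 | 300 | 300 | 0 | 0% |
| 330 | 1.0 | 300 | 330 | 30 | 10% |
| 360 | 1.0 | 300 | 360 | 60 | 20% |
| 300 | 0.8 | 240 | 240 | 0 | 0% |
| 330 | 0.8 | 240 | 264 | 24 | 10% |
| 360 | 0.8 | 240 | 288 | 48 | 20% |

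For individual injections, take the 40:30:30 split of Section 9.7 and the rounding to 5 units of Section 9.8.2. At f = 1.0 and H = 360, the table gives 120/90/90 U. The other two sections give 144, 108 and 108, which round to 145/110/110 U. If H were below S, the sign would reverse.

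**The case against.** The best reply is that the mismatch lies in one column heading. The text under the table uses screening to classify the entry regimen and HbA1c, and applies the factor at Visit 4. A site could take the table as supplying only the factor and Section 7.1.7.1 as supplying the base. It could also read the heading as the dose of the screening regimen, which subjects keep until Visit 4 (Sections 7.1.5 and 9.3). This is a reasonable reading, and for a subject with a constant TDD the two rules agree exactly. It shows that divergence between sites is a possibility and not a demonstrated effect. It does not remove the ambiguity, because the protocol nowhere states that reading and the operative table says something else.

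A reader might infer from the lead-in's dose-verification purpose that the two TDDs are expected to differ. Verifying a dose may equally mean confirming it. Attachment 1 does list adjusting or recording the insulin dose during lead-in, so change is possible, but it is not quantified. A reader might also be struck that the 20% gap in the largest example matches the table's own 20% reduction. That match follows only from choosing 360 U.

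The amendment summary shows that Section 9.4 and the SMBG heading of this table were edited. I place no weight on that; the conflict stands in the current text alone.

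**Conclusion.** The point holds as an internal inconsistency in a dosing rule. Table IBHD.9.3 and Sections 7.1.7.1 and 9.4 name different TDD sources, about two to three weeks apart, with no order of precedence. The relative difference in starting dose equals the relative difference between the two TDDs. On the assumed values it runs from 0 to 60 U/day at 1:1 and from 0 to 48 U/day with the 20% reduction. The documents support no particular value in that range, and zero is possible.

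A stronger inference would be that inconsistent starting doses add noise to, or bias, the trial's result. The documents do not support it. Both arms go through the same transition with weekly adjustment, titration continues afterwards, CSII doses are recalculated at Visit 6 (Section 9.8.1), and the primary endpoint is at Week 26. The inconsistency does not by itself bias the CSII versus MDI comparison, and it does not affect sample size, power or alpha. The case for correcting it rests on the clarity and safety of the first dose.

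**What to change.** Reconcile the dose-column heading of Table IBHD.9.3 with Sections 7.1.7.1 and 9.4, so that all three name one TDD source, including the days on which it is measured. The sponsor and investigators should choose the source; this review does not say which is right. Section 7.1.7.1 should also carry an explicit visit anchor, since at present only Section 9.4 ties the 3 days to Visit 4. A cross-reference from Section 9.7 to the sentence that defines the TDD would prevent a recurrence.

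The cost is a heading or text correction and a notice to sites. No analysis, sample size or data collection changes.

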9.7.1. Dosing Using U-100 Insulin Syringes

The units marked on a U-100 insulin syringe do not accurately reflect the unit dose of U-500R insulin because U-500R is 5 times more concentrated than U-100 insulin, and thus only one-fifth of the volume is needed to give an equivalent dose to U-100 insulin. Site personnel should instruct subjects on the dose conversion of calculated U-500R to the U-100 insulin syringe unit markings (examples below and conversion charts are also provided in the U-500R package insert and Subject Information on U-500R).

The U-100 insulin 0.5 mL syringes should be used for administration for all U-500R doses ≤250 U. All U-500R doses >250 units should be administered using 1.0 mL U-100 insulin syringes.

For example:

- 155 units of U-500R has a volume equivalent to 31 units markings on a 0.5 mL U-100 insulin syringe (155 divided by 5=31).
- 100 units of U-500R has a volume equivalent to 20 units markings on a 0.5 mL U-100 insulin syringe (100 divided by 5=20).
- 300 units of U-500R has a volume equivalent to 60 units markings on a 1.0 mL U-100 insulin syringe (300 divided by 5=60).

9.7.2. CSII Training

Subjects randomized to the CSII treatment arm will be trained on the use of the OmniPod U-500 system after randomization at Visits 5 and 6 (Weeks 1 and 2). CSII training will include but not be limited to pre-pump training regarding basal rates and bolus dosing, initial PDM and Pod setup, setting basal rates (including temporary basal rate) and boluses (CHO counting, fixed dosages or meal sizes), and responding to hazard alarms. The OmniPod U-500 system basics of pump usage (ie, basal rates, boluses, and filling Pods) will be introduced to subjects at Visit 5 (Week 1) and the hands on training will occur at Visit 6 (Week 2) (Section [7.1.7.3.](#)).

9.7.3. Intensified Dose Titration Period

The 12-week intensified dose titration period of the trial will extend from Visit 6 (Week 2) to Visit 13 (Week 14) and will include **investigator-driven** dosage titration according to the titration algorithms (Sections [9.8.1.1](#) and [9.8.2.1](#)) at weekly intervals starting on Visit 6 through 8 (Weeks 2 through 4) and biweekly starting at Visit 9 through 13 (Weeks 6 through 14) ([Attachment 1](#)). Additional dosage titrations per algorithms may be made more frequently if needed per investigator's judgment during this period.

9.7.4. Maintenance Dose Titration Period

The 12-week maintenance dose titration period of the trial will extend from Visit 13 (Week 14) to the final visit, Visit 17 (Week 26) or ET visit. Dose titrations by the **investigator** will be completed in an identical manner to those during the intensified dose titration period (Sections [9.8.1.1](#) and [9.8.2.1](#)) but will be at 3-week intervals ([Attachment 1](#)). Additional dosage titrations per algorithms may also be made more frequently if needed per investigator's judgment during this period.

9.8. Treatment Periods

9.8.1. CSII

The OmniPod U-500 system is designed to deliver U-500 insulin in insulin units without converting to U-100 insulin 'pump units' (Section [7.2](#)). Beginning at Visit 6 (Week 2), all CSII subjects will be instructed to change their OmniPod U-500 system Pod every 2 to 3 days (depending on TDD) during the treatment period. Subjects will be instructed to inspect Pod cannula insertion sites for signs of redness, swelling, or leakage and to respond to any CSII alarms (Bolderman et al. 2013).

For subjects randomized to CSII:

- The OmniPod U-500 system Pod should be filled in the clinic with U-500R during Visit 6.
- The highest 24-hour TDD from the past 3 days will be utilized for calculation of the CSII doses.
- 50% of the TDD will be basal split into 2 rates:
 - 2100 to 0600 hours 10% basal rate reduction
 - 0600 to 2100 hours for the calculated basal rate
- 50% of the TDD will be bolus split into the following ratio:
 - 40:30:30 (Section 9.8.1.3) for fixed bolus doses.
 - Suggested initial setting for insulin: CHO ratio should be programmed between 1:3 and 1:5.

9.8.1.1. CSII Treatment Group Algorithms

Subjects in the CSII group will have their basal rates (Table IBHD.9.4) and bolus doses (Table IBHD.9.5) adjusted at each study visit (office and telephone) **by the investigator** according to the CSII titration algorithms. Investigators may deviate from the algorithms, if deemed necessary, for the safety or well-being of the subject (that is, due to illness or other safety concern). Any major deviation from the algorithm must be discussed with Lilly. The CSII bolus titration scheme (Table IBHD.9.5) will be divided into 2 dosing bins: TDD <400 units and TDD \geq 400 units. Subjects will have their U-500R adjusted according to the TDD at the time of adjustment.

Subjects taking <400 units TDD at Visit 6 (Week 2) should use a 1:10 correction factor with a target of 100 mg/dL starting at 25 mg/dL above target for all mealtime boluses. Subjects taking \geq 400 units TDD at Visit 6 (Week 2) should use a 1:5 correction factor with a target of 100 mg/dL starting at 25 mg/dL above target for all mealtime boluses. If, in the opinion of the investigator, the subject would benefit from a different correction factor, the investigator should discuss this with the Sponsor.

Note: Subjects should be instructed to hold their U-500R bolus dose if a meal is skipped.

Table IBHD.9.4. Basal Titration Scheme for CSII

Median SMBG (mg/dL)	Titration of Corresponding Basal Rate for All Dose Ranges ^a
<80	-5%
80-140	0
141-190	+5%
191-230	+10%
>230	+15%
3-day median SMBG measure	Dose adjusted
Pre-Morning Meal, 0300 hours ^b	Overnight infusion
Pre-Evening Meal	Daytime infusion

Abbreviations: CSII = continuous subcutaneous insulin infusion; SMBG = self-monitored blood glucose.

^a Any plasma glucose (SMBG or lab) measurement <50 mg/dL or ≤70 mg/dL at 0300 hours during the week, investigator should reduce corresponding basal dose by 10-20% as soon as it occurs or notification of the reading occurs.

^b If subject acquires more than the 2 initial basal rates, adjusted basal doses will continue to be based on the pre-morning meal and 0300 hours, and pre-evening meal SMBG.

Table IBHD.9.5. Bolus Titration Scheme for CSII

Median SMBG ^{a,b,c} (mg/dL)	Dosing Bin for TDD <400 U Titration (U)	Dosing Bin for TDD ≥400 U Titration (U)
<80	-5	-10
80-140	0	0
141-190	+2.5	+5
191-230	+5	+10
>230	+7.5	+15
3 Day Median SMBG ^d	Adjusted Dose	
Pre-midday meal	Pre-morning meal	
Pre-evening meal	Pre-midday meal	
Bedtime ^e	Pre-evening meal	

Abbreviations: CSII = continuous subcutaneous insulin infusion; CHO = carbohydrate; SMBG = self-monitored blood glucose; TDD = total daily dose; U = units.

^a Each of the 3 bolus doses is adjusted independently based on the median of 3 corresponding SMBG values (preferably most recent 3 days).

^b Any plasma glucose (SMBG or lab) measurement <50 mg/dL, investigator should reduce corresponding bolus dose by 10-20% as soon as it occurs or notification of the reading occurs.

^c If the algorithm adjustment leads to overlapping basal and bolus adjustments, the investigator has the discretion to reduce the bolus adjustment for safety.

^d If the subject is using CHO meal sizes or CHO counting for boluses and their SMBGs are not in the target range for the corresponding meal at the visits (telephone or office) for algorithm titrations, then the principal investigator should adjust (increase or decrease) the insulin CHO ratio by approximately 10% to 15%.

^e In the event that nocturnal hypoglycemia occurs requiring a reduction in the overnight basal rate, the investigator may reduce the pre-dinner dose even if the bedtime SMBG median is in the target range of 80-140 mg/dL.

Note: All CSII basal and bolus doses will be rounded to the nearest 0.25 units.

9.8.1.2. CSII Basal Rate

The overnight basal rate from 2100 to 0600 hours is adjusted based on the median fasting pre-breakfast SMBG from the past 3 values (most recent 3 days recommended) and the basal rate from 0600 to 2100 hours is adjusted based on pre-dinner SMBG (most recent 3 days recommended). The principal investigator may increase the number of basal rates up to 4 basal rates during the trial, if in the investigator's opinion the subject needs further individualization of basal rates based on blood sugar trends, such as nocturnal hypoglycemia or the dawn phenomenon indicating a need for the change(s).

